#### **Research MRI utilizing Non-contrast MRI**

A Non-contrast MRI will be performed in the standard manner. Upon arriving to the radiology department for the MRI, a pregnancy test will be administered for all female participants of child bearing potential. An institutional MRI screening form will be given to each patient and parent and reviewed with the MRI technologist. If there is any retained metal (pacemaker, metallic bb, orthopedic hardware), MRI will not be performed.

Table 3 – Patient Schedule of Assessment												
Procedure Step		Pre-Screen Visit	Week 1 +/- 10 d	Week 2 +/- 10 d	Week 3 +/- 10 d	Week 4	Week 5	Week 6 +/- 1wk	Week 12 +/- 1wk	Month 6* +/- 1wk	Month 9 +/- 1wk	Month 12 +/- 2wk
Non-contrast MRI, MRI with and without contrast, or dGEMRIC for OCD lesion ( standard of care )	X A								X R			
Initial & Follow-up x-rays dependent on symptoms ( standard of care )	X							X D	X D	X D	X D	
Informed Consent ( research )	X B											
Inclusion / Exclusion Criteria confirmation ( research )		X R										
Patient Reported Outcomes IKDC, KOOS-child ( research )		X R					X R	X R	X R	X R	X R	
Randomization ( research )		X										
Compliance Survey ( research )		X R	X R	X R	X R	X R	X R					
Physical exam ( research for PRP arm patients weeks 1, 2, & 3 and standard of care visits for both treatment arms for weeks 6, 12 and months 6, 9, 12)		X C	X C	X C			X	X	X	X	X	
Blood draw & processing using the Harvest PRP kit( research )		PRP only	PRP only	PRP only								
Autologous PRP Injection ( research )		PRP only +/- 7days	PRP only +/- 7days	PRP only +/- 7days								
Hinged Brace in extension for 6 wks ( standard of care )		X	X	X	X	X	X					

X = occurs for both patient groups;

A = Standard of care visit to pre-screen for minimal inclusion criteria; all patients will undergo the same standard of care MRI procedure

B = Patient consenting can occur at either the initial screening visit, or when given the option to take the consenting material home for review they will be consented at their 2nd visits if they choose to enroll in the study.

C = PRP Arm – Physical Exam will be performed for research only and will be take place prior to the injection of PRP.

D = X-rays are performed as standard of care depending on the conditions of each individual patient.

R=Research \* 6 months from initial visit

## **Participant Discontinuation Criteria**

Patients may be withdrawn from the trial for one of the following reasons:

1. Noncompliance with the protocol procedures
2. The patient has been given other or additional treatment, which may interfere with the study treatment (such as intra-articular steroid injection).
3. The patient wishes to withdraw from the trial
4. A severe adverse reaction by treatment applied is evident. Such as joint infection which requires IV antibiotics and possible surgical irrigation and drainage.
5. Patient becomes pregnant prior to completion of the third injection
6. Patients receiving conservative treatment whose lesion becomes unstable, requiring surgery during the study period will be excluded from participating in the remainder of the study
7. The investigator may withdraw patients from the trial if it is in the best interest of the patients. The reason for withdrawal shall be clearly described and the patient shall, whenever possible irrespective of the reason for withdrawal, as soon as possible be called for a final visit. All relevant assessments shall be completed, preferably according to the schedule for the final visit.

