## **Informational patient brochure/Compliance Surveys/ Baseline and Follow-up KOOS and IKDC surveys/Clinical Assessments**

An informational brochure (see attached) will be used to assist in the recruitment of eligible patients. The brochure will describe the autologous platelet rich plasma treatment, process, risks, appointment information and post procedure information.

Patients randomized to the PRP Treatment arm will receive a Pre and Post-Injection Instruction handout (see attached). The handout describes how the patient should prepare for the PRP injections and what to expect after the injection.

The study personnel who consents the patient will request the patient's and parent's email addresses which will be used to send out the weekly and monthly surveys.

For the first 6 weeks of the study, all patients will receive a weekly Compliance Survey (see attached) created by the Sports Medicine physicians to validate compliance with 1. non-weight bearing, 2. wearing a brace, 3. at home PT exercises, and 4. no high impact activity.

**KOOS/IKDC surveys:** All patients will receive a baseline survey and repeat surveys at 6 wks, 12 wks, 6 m, 9m, and 12 months, which is considered standard of care, on the CHCO main campus or one of the following satellite locations (South, Parker, Centennial, Uptown/St Joseph's or Broomfield). The surveys will include the following outcome scales: Pedi IKDC and KOOS-child.

The Pedi-IKDC is a modified version of the widely used International Knee Documentation Committee (IKDC) Subjective Knee Form, which is a knee specific measure of symptoms, function and sports activity. The Pedi-IKDC was developed for use with children and adolescents ages 10-17. The reliability and validity of the Pedi-IKDC has been demonstrated to be acceptable in young patients with a variety of knee disorders.

Similarly, the KOOS – child is a pediatric version of the Knee Injury and Osteoarthritis Outcome Score (KOOS). The KOOS-child score is subdivided and scored in five categories: Pain, Other Disease-Specific Symptoms, Activities of Daily Living Function (ADL), Sport and Recreation Function and Knee-related Quality of Life (QOL).

[http://www.actaorthop.org/sup\\_files/5292.pdf](http://www.actaorthop.org/sup_files/5292.pdf)

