### **6 month Research MRIs**

- If the patient received their initial diagnostic MRI by a Non-contrast MRI, the patient will receive a Non-contrast MRI at their 6 month research MRI visit.
- If the patient received their initial diagnostic MRI by a dGEMRIC MRI, the patient will receive a dGEMRIC MRI at their 6 month research MRI visit.
- If the patient received their initial diagnostic MRI by a MRI with and without contrast, the patient will receive a Non-contrast MRI at their 6 month research MRI visit.

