### **Proposed statistical analysis for Aim 1: Cartilage healing**

The T1GD value on dGEMRIC measures GAG content in cartilage. Higher T1GD values are associated with higher GAG content in the tissue, a positive measure of cartilage health. We assume that the value is approximately normal.

We plan to fit a general linear mixed model [39] for the outcome of T1GD. Predictors will include the visit at which the T1GD test was performed (initial MRI and 6 months), whether the site was weight bearing or not, and whether the side was affected or not, and the treatment group. Age will be included as a covariate. An unstructured covariance will be used to account for correlation between T1GD measurements on the same participant. Jackknifed-studentized residuals will be examined to assess normality, and transformations will be applied as appropriate.

We will test the null hypothesis of no time by treatment by weight bearing surface by affected side interaction. Given a non-significant interaction, we will test the main effects of time and treatment, comparing the difference between the weight-bearing and non-weight bearing surface for the affected and non-affected sides. Estimates, 95% confidence intervals, and p-values will be produced. All hypothesis tests will be performed using the Wald test with Kenward and Roger degrees of freedom[40] . Hypothesis tests will be performed at the Bonferroni corrected alpha of  $0.05/3 = 0.017$ .

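### Discontinuation means leaving the trial, with no option to stop treatment and stay in follow-up; the one mandatory exclusion, surgery for an unstable lesion, most naturally covers the control arm only

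*Combined protocol and SAP*

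**What the plan says.** The Participant Discontinuation Criteria list seven reasons under the sentence "Patients may be withdrawn from the trial for one of the following reasons". They include noncompliance (item 1), a severe reaction to treatment (item 4), pregnancy before the third injection (item 5) and, as item 2, "The patient has been given other or additional treatment, which may interfere with the study treatment". Item 7 adds a general discretion: "The investigator may withdraw patients from the trial if it is in the best interest of the patients". The same item asks that the reason be described and that, whatever the reason, the patient be called for a final visit if possible, with assessments done "preferably according to the schedule for the final visit".

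Item 6 is worded differently. It reads "Patients receiving conservative treatment whose lesion becomes unstable, requiring surgery during the study period will be excluded" from the remainder of the study.

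Three other parts of the plan bear on this:

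- **Compliance.** "For the first 6 weeks of the study, all patients will receive a weekly Compliance Survey".
- **Imaging.** There is one follow-up MRI, at 6 months. Its type follows the initial scan: where that scan was a non-contrast MRI or an MRI with and without contrast, "the patient will receive a Non-contrast MRI at their 6 month research MRI visit". The Aim 1 model has only two time points: "Predictors will include the visit at which the T1GD test was performed (initial MRI and 6 months".
- **Attrition.** The Power Analysis expects to lose up to two patients per arm over 12 months and enrols 12 per arm so as to keep 10.

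The Randomization section says that the randomised assignment, coded 1 or 2, goes to the statistician. The Data Analysis Plan does not say which patients are included, or what happens to data after withdrawal or surgery.

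**The concern.** When stopping treatment also ends data collection, patients drop out of the comparison because of what happened to them after randomisation. If those events are related to healing and arise differently in the two arms, the patients who remain are no longer the groups that were randomised. Patients, parents and the injecting physician know the assignment, so discretionary withdrawals could also differ by arm.

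Item 6 is the sharpest case. It ends follow-up at the clearest clinical failure in this disease, and the closing summary of the protocol names avoiding surgery as a possible benefit of faster healing. With 12 patients per arm, one or two such losses are a visible share of the data.

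**Working it through.** **1. The plan's own allowance.** Ten evaluable patients per arm with up to 2 of 12 lost: 10 / (1 - 2/12) = 12 per arm, 24 in total. This reproduces the enrolment goal. It covers how many are lost, not why.

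**2. What each rule does.**

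| Event | Force | Arm mainly affected |
|---|---|---|
| Noncompliance (item 1) | may | either; the PRP arm has three more procedures to miss |
| Other treatment (item 2) | may | either |
| Severe reaction to treatment (item 4) | may | mainly PRP |
| Pregnancy before third injection (item 5) | may | in effect PRP |
| Instability needing surgery, conservative treatment (item 6) | will | control, on the natural reading |
| Same event in a PRP patient | at most items 2 or 7: may | PRP |

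The natural reading of item 6 rests on the labels used elsewhere. The assignment log and the treatment schedule both use *conservative* for the control arm.

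**3. Aim 1 timing.** Compliance is surveyed up to week 6, and the follow-up MRI is at month 6, about week 26. The gap is 26 - 6 = 20 weeks. The model has no visit between the initial MRI and month 6, so a patient withdrawn in that interval contributes a baseline value only. At the assumed correlation of 0.2, baseline explains 0.2 x 0.2 = 0.04 of the variance at follow-up, so it says little about the missing value. The exit visit does not replace it: a scan at exit is not a 6-month value, and the month 12 visit has no MRI.

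**4. Aim 2 timing.** The model uses five survey visits: weeks 6 and 12, and months 6, 9 and 12. A patient withdrawn between week 12 and month 6 puts three of the five at risk. Whether they are lost is unclear. Research Methods and the survey section treat these visits as standard of care, Table 3 labels the surveys as research, and no rule says that they are used after withdrawal.

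**5. Illustrative size for Aim 1.** The documents give no withdrawal rate by reason and no share of patients with dGEMRIC, so these are assumptions. Let k patients leave one arm before month 6, out of n with dGEMRIC, and let them differ from the rest of their arm by d = 42.5 to 85 ms (half to all of the planned effect). The as-randomised contrast then differs from the retained-patient contrast by k x d / n.

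- n = 12, k = 1: 42.5/12 = 3.5 ms to 85/12 = 7.1 ms.
- n = 12, k = 2: 2 x 42.5/12 = 7.1 ms to 2 x 85/12 = 14.2 ms.
- n = 6, k = 1: 42.5/6 = 7.1 ms to 85/6 = 14.2 ms.

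Taking 85 ms as the contrast among retained patients and n = 12, the as-randomised contrast would be 81.5 to 70.8 ms if PRP patients with less benefit leave, or 88.5 to 99.2 ms if controls who do worse leave.

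Compared with the standard error for n = 12:

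- 6-month values only: 50 x sqrt(2/12) = 20.4 ms; ratios 3.5/20.4 = 0.17 to 14.2/20.4 = 0.69.
- Change from baseline: 50 x sqrt(2 x (1 - 0.2)) x sqrt(2/12) = 25.8 ms; ratios 3.5/25.8 = 0.14 to 14.2/25.8 = 0.55.

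For n = 6, the 6-month standard error is 50 x sqrt(2/6) = 28.9 ms, with ratios of 0.25 to 0.49.

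**The case against.** Several points on the other side stand.

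- **Permissive wording.** Items 1, 2, 4, 5 and 7 allow withdrawal but do not require it, and no compliance threshold is set. Investigators could keep most patients. This does not reach item 6.
- **Assigned arm.** A reader might infer that patients could be analysed by treatment received. The documents do not support that. The statistician receives the randomised assignment, stays blinded to its meaning until shortly before submission, and is given no treatment-received variable. Only a statement of who is included is missing.
- **Surveys.** A reader might infer that all surveys after withdrawal are lost. Because the visits are described as standard of care, they may well still take place. The labels conflict, and using the data after withdrawal would need consent.
- **Scope of item 6.** A reader might take it as certain that item 6 is confined to controls. The Specific Aims and the treatment section show that PRP patients also receive conservative care, so a both-arms reading is possible. The ambiguity is itself a reason to reword.
- **Frequency.** Entry is limited to stable stage 1 or 2 lesions with open physes, and the protocol says that such patients typically heal within 12 months. Item 6 events may be uncommon.
- **Model.** The mixed models keep data collected before withdrawal, which helps Aim 2. It helps Aim 1 little, for the reason in step 3.
- **Limits of the remedy.** Hardware after surgery bars the MRI, and a scan that is possible will partly show the surgery. Whether to use such values is a choice about the question being asked. Patients who leave because they dislike their assignment are not reached either.

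**Conclusion.** The point holds as a gap in the discontinuation rules, and it is inexpensive to close. Followed as written, the plan ends scheduled follow-up at events that may be related to outcome. For surgery after instability it does so by a mandatory rule that, on its natural reading, applies to one arm. For Aim 1, a withdrawal before month 6 removes the only post-treatment measurement.

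The size is unknown. The illustration of 3.5 to 14.2 ms rests on an assumed difference between leavers and stayers. Its upper end also puts both of the two losses allowed in one arm before month 6, although the plan's allowance runs over 12 months and losses after month 6 cost Aim 1 nothing. Even then the shift stays below 0.7 of a standard error.

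A reader might infer that the rules bias the trial for or against PRP. The documents do not support a direction: item 6 would tend to remove control failures and flatter the control arm, while items 4 and 5 would mainly remove PRP patients and could work the other way.

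**What to change.** In the Participant Discontinuation Criteria, separate stopping study treatment from withdrawing from the study.

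- For items 1, 2, 4, 5 and 6, in both arms, keep the patient in the scheduled 6-month MRI (unless contraindicated, for example by pregnancy or hardware), in the surveys to month 12 and in adverse event follow-up.
- End data collection only on withdrawal of consent (item 3) or on the investigator's judgement under item 7. When to stop injections or bracing remains a clinical decision.
- Word item 6 identically for both arms, and report instability or surgery by arm with its date, including where the MRI cannot be done.
- Add one sentence to the Aim 1 and Aim 2 analyses: all randomised patients with data are included in their assigned arm.

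The cost is protocol and consent wording. The sample size does not change, and every assessment is already scheduled. The downside is that some follow-up values will reflect incomplete treatment or later surgery, so the estimate may move in either direction, and the MRI may remain unobtainable for some patients.

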### **3. Background:**

#### **a. Osteochondritis dissecans:**

Osteochondritis dissecans (OCD) is an osteochondrosis characterized by osseous necrosis followed by reossification and healing. There are both juvenile and adult forms of this condition. The most common anatomic location for this to occur is the knee, with the most frequent involvement being the medial femoral condyle. This can also occur in the elbow, ankle, or hip. The etiology is unknown though repetitive micro trauma and or ischemia are postulated as possible inciting factors. MRI is frequently used in the diagnosis of osteochondral lesions associated with OCD. Lesions can be stable or unstable. Stable lesions in patients with open physis, juvenile form, are typically treated conservatively, while unstable lesions traditionally require surgical intervention. The adult form is similar, though the patient's physis are fused. This process affects adolescent males three times more than females.

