## **Treatment Regimens and Dosing**

All eligible patients will be randomized to a treatment or conservative therapy group. Those within the conservative therapy group will be fitted with a hinged brace locked in extension, with weight bearing as tolerated and crutches for those with painful to weight bear, complete rest from impact activities, progressing to weight bearing as tolerated for 6 weeks, and then followed according to the Orthopedic department's protocol for OCD.

The PRP treatment group will receive three injections per randomization table into the symptomatic knee, they will also be fitted with a hinged brace locked in extension, with weight bearing as tolerated and crutches for those with pain upon weight bear, complete rest from impact activities with progression to weight bearing as tolerated for 6 weeks, and then followed according to the Sports Medicine department's protocol for OCD. Study subjects in the PRP treatment arm will receive a total of 3 intra-articular injections, one week apart +/- 10 days. All subjects will have a physical exam performed to assess their knee function.

If a patient has bilateral symptomatic knee osteochondritis dissecans, the more symptomatic side will be injected while the less symptomatic side will not be injected, the patient will then follow the same treatment regimen as the treatment group on the treated side.

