**Conservative treatment participants:** A total of 5 visits (6 visits, if consent is done as a separate visit) are expected during a 12-month time period for patient follow-up. The first visit will include initial assessment and possible recruitment. The second through fifth visits will include patient reported surveys, physical examination and x-rays to assess the injury in accordance with the standard of care at CHCO. MRI obtained prior to enrollment for initial evaluation of the knee is performed as standard of care in the management of knee OCD. The research MRI performed at 6 months post treatment will be obtained to assess cartilage healing utilizing physiologic imaging of cartilage with the dGEMRIC technique or a Non-contrast MRI of the knee. **Please refer to the patient schedule matrix, Table 3, below.**

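### Discontinuation item 6 ends scheduled survey follow-up when a lesion becomes unstable and needs surgery, does not make clear which arm it covers, and is matched by no analysis of surgery by arm

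*Combined protocol and SAP*

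**What the plan says.** **The rule.** Under Participant Discontinuation Criteria, the lead-in says that patients *may* be withdrawn for the listed reasons. Item 6 is worded as an obligation: "Patients receiving conservative treatment whose lesion becomes unstable, requiring surgery during the study period will be excluded from participating in the remainder of the study". Item 7 adds that the reason for withdrawal must be described and that the patient shall, "whenever possible irrespective of the reason for withdrawal, as soon as possible be called for a final visit", with the relevant assessments completed then.

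**Who is covered.** The section on treatment schedules heads the control arm's visits "Conservative treatment participants". Treatment Regimens and Dosing describes the control arm with "Those within the conservative therapy group will be fitted with a hinged brace locked in extension", and Table 1 labels it Conservative. But of the PRP arm the same dosing section says "they will also be fitted with a hinged brace locked in extension", and Aim 1 describes PRP as combined with conservative therapy. The Background uses the term for non-operative care in general: "Stable lesions in patients with open physis, juvenile form, are typically treated conservatively, while unstable lesions traditionally require surgical intervention".

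**What is scheduled.** All patients have a baseline survey and "repeat surveys at 6 wks, 12 wks, 6 m, 9m, and 12 months". The Aim 2 model lists those five post-baseline visits. Patient and parent contacts are collected at consent as "email addresses which will be used to send out the weekly and monthly surveys".

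**What the analysis plan says about surgery.** Nothing from the Data Analysis Plan through the Power Analysis defines an analysis set, a rule for patients who have surgery or a missing-data rule, or reports surgery by arm. The closing section on knowledge to be gained names sparing patients surgery as a hoped-for benefit.

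**The concern.** A lesion that becomes unstable and needs surgery is the clearest treatment failure in this trial. A rule that ends participation at that moment makes missing data depend on the outcome. If it binds one arm only, the missing data depend on the arm as well. The later Aim 2 comparisons would then be made among patients from whom the worst courses have been removed, possibly on one side only. The protocol also does not say whether a PRP patient in the same position leaves or stays, so study staff could handle the same event differently. Finally, the trial could report without showing whether lesions went on to surgery more often in one arm.

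**Working it through.** **1. Coverage.** Three places use the conservative label for the control arm: Table 1, Treatment Regimens and Dosing, and the schedule section. On that reading, a PRP patient needing surgery falls only under the discretionary items: item 2 (other or additional treatment) and item 7 (investigator's judgement). Against that, Aim 1 and the dosing section give the conservative regimen to both arms, and the Background contrasts conservative treatment with surgery. Control-only is therefore the more natural reading, but it is not settled. Follow-up stops at failure on both readings.

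**2. Surveys lost.** The Aim 2 model uses weeks 6 and 12 and months 6, 9 and 12.

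| Exclusion falls | Modelled surveys lost (of 5) |
|---|---|
| before week 6 | 5 |
| weeks 6 to 12 | 4 |
| week 12 to month 6 | 3 |
| months 6 to 9 | 2 |
| after month 9 | 1 |

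The final visit in item 7 returns at most one score, off schedule and only where possible.

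**3. The plan's own allowance.** The Power Analysis targets 10 effective patients per arm and expects to lose up to two: 10 + 2 = 12 per arm, and 2 × 12 = 24. This reproduces the enrolment goal. It allows for the number lost, not for losses selected on outcome or arm.

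**4. What the mixed model can do.** It keeps scores from before surgery. Its estimates are then valid only if, given those scores and the covariates, missingness does not depend on the unseen scores. The plan does not state this assumption. It is doubtful here because exclusion follows lesion instability, which is not in the model, and least credible when few scores precede failure.

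**5. Illustration of scale.** The documents give no surgery rate, survey SD or score gap for failures, so these inputs are assumptions. Suppose *k* of 12 controls are excluded after week 12. Let *g* be their month-12 gap below the other controls, and *d* the gap already visible at weeks 6 and 12, both in SD. Let *r* be the correlation between any two surveys (equal correlations).

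- Shift = (*k*/12) × (*g* − *B* × *d*), with *B* = 2*r*/(1 + *r*).
- *B* = 0.6/1.3 = 0.46 at *r* = 0.3; 1.0/1.5 = 0.67 at *r* = 0.5; 1.4/1.7 = 0.82 at *r* = 0.7.
- *k* = 1, no early gap (*d* = 0): 1/12 = 0.083 SD for *g* = 1; 2/12 = 0.167 SD for *g* = 2.
- *k* = 1, full gap already visible (*d* = *g*): 0.045, 0.028 and 0.015 SD for *g* = 1; 0.090, 0.056 and 0.029 SD for *g* = 2 (*r* = 0.3, 0.5, 0.7).
- Standard error, 12 versus 11: √(1/12 + 1/11) = 0.417 SD.

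The range is 0.015 to 0.167 SD, or about 0.04 to 0.40 of a standard error (0.015/0.417 and 0.167/0.417). This is a month-12 contrast. Aim 2 tests the time-trend-by-treatment interaction first, so the figures show scale and not the effect on that test.

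**6. Direction.** If only controls are excluded, the control mean is probably flattered and a PRP benefit understated. If PRP patients stay in and are measured after surgery, the direction is uncertain. If both arms are covered, it depends on how many fail in each.

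**The case against.** The case for leaving the text nearly as it is has weight. Only stable Di Paola stage 1 or 2 lesions are enrolled, and the protocol's background says that such patients typically heal within 12 months, so nothing suggests that surgery will be common. Two losses per arm are already allowed for, and the illustrated shift from one loss is under half a standard error. Much of the raw material exists: withdrawal reasons must be described, treatment assignment is recorded, and Di Paola is scored on both scans. Adverse-event reporting might also capture surgery, though the text does not say so. Item 2 could cover surgery in either arm, so the contrast is mandatory against discretionary, not covered against uncovered. The surveys are called standard of care in the survey section (though research in Table 3), so some may still be completed in clinic. Aim 2 is not the primary endpoint. And stopping at surgery is itself a defensible target of estimation.

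Most of this stands, and it limits the point to an inexpensive improvement. It does not remove the gap: item 6 still takes later surveys out of the study, its coverage is still open, and no analysis uses the withdrawal reasons.

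A reader might infer more than the documents support:

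- *That the rule would manufacture a PRP benefit.* On the control-only reading the likely bias runs the other way.
- *That the arms are definitely treated differently.* The wording leaves both readings open.
- *That failures vanish without trace.* A final visit is called for and the reason must be described.
- *That the primary T1GD result is thereby shown to be distorted.* The documents give no rate or timing of surgery from which to judge that.

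**Conclusion.** The concern holds as a gap in the data-collection rule and in reporting. As written, item 6 makes survey follow-up end because treatment failed, with unclear and possibly unequal coverage of the arms, and nothing elsewhere restores the lost schedule or says how surgery is analysed. The loss per patient is exact: one to five of the five modelled surveys. The effect on the comparison cannot be sized from the documents. The illustration assumes one excluded control, a gap of 1 to 2 SD and correlations of 0.3 to 0.7; on those assumptions it is modest, and it scales with the number excluded. This should be fixed because the remedy costs little, not because the trial is shown to be seriously biased.

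**What to change.** 1. **Reword item 6.** State which arm or arms it covers, reconcile *may* in the lead-in with *will* in the item, and make it one arm-neutral data-collection rule. Patients in either arm who have surgery stay in follow-up for the surveys already scheduled, unless they withdraw under item 3, and are analysed in the arm assigned.
2. **Add a treatment-failure table.** Report surgery, and progression to Di Paola grade 3 or higher on completed scans, by arm. With 12 per arm this is descriptive only: 0 versus 2 failures gives a two-sided Fisher p of 2 × 66/276 = 0.48, with exact 95% intervals of 0–26% and 2–48%.
3. **Show Aim 2 both ways.** Present each of the four outcomes with all data and with data up to surgery only, and say in advance which is the main analysis.

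The cost is an amendment to one item, one table and one additional analysis per Aim 2 outcome. The survey schedule and email route already exist. There are two downsides. Scores after surgery partly reflect the repair, which is why both versions are needed. And the primary T1GD contrast is not recovered. The change concerns data collection and reporting only; when and how a lesion is operated on is left untouched.
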